Study Protocol Document

Study Title: Diagnostic and Prognostic Value of Reticulated Platelet Fraction in Patients With Ventilator-Associated Pneumonia: A Prospective Observational Study

Protocol ID: KSH-RP-VAP-2025-01

Version Number: 1.0

Date: June 2025

1. Background and Rationale

Ventilator-associated pneumonia (VAP) is a common nosocomial infection in ICU patients undergoing mechanical ventilation for more than 48 hours. Traditional inflammatory markers like CRP and procalcitonin are commonly used but have limitations in early diagnosis. Reticulated Platelet Fraction (RP%) is an emerging biomarker with potential utility in early infection diagnosis and prognosis. This study aims to evaluate the diagnostic and prognostic value of RP% in VAP.

2. Objectives

Primary Objective:

- - To assess the diagnostic accuracy of RP% in patients with VAP.

Secondary Objectives:

- - To evaluate the association between RP% and 28-day mortality.
- - To explore correlations with SOFA scores and antibiotic de-escalation.

3. Study Design

This is a single-center, prospective observational cohort study to be conducted in a tertiary-level ICU. Data will be collected prospectively from patients diagnosed with VAP.

4. Population

Inclusion Criteria:

- - Age \geq 18 years
- - Mechanically ventilated >48 hours
- - Diagnosed with VAP

Exclusion Criteria:

- - Pneumonia at ICU admission or as primary reason for intubation
- - MV duration <48 hours
- - Pregnancy or lactation

- - Hematologic, oncologic, or autoimmune conditions within the past 4 weeks
- - Immunosuppressive therapy or chemotherapy

5. Data Collection and Laboratory Procedures

RP% will be measured via Sysmex XN-1000 using EDTA blood samples, processed within 4 hours. Routine lab values (CRP, PCT, WBCs, etc.) and clinical data (demographics, MV duration, SOFA scores) will be collected from electronic records. Serum for CRP and PCT will be processed via Roche Cobas 8000 after centrifugation.

6. Sample Size

Based on a predicted correlation coefficient ($r=0.5$) between RP% and PCT, a power analysis ($\alpha=0.05$, power=0.95) using G*Power resulted in a required sample size of 38. Considering a dropout margin, a total of 42 patients will be enrolled.

7. Statistical Analysis

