Data will be analyzed using SPSS v26. Normality will be assessed via Kolmogorov-Smirnov test. Comparisons will be made using independent samples t-test or Mann-Whitney U test for continuous variables, and Pearson chi-square for categorical data. Correlations will be examined using Pearson or Spearman correlation based on data distribution. A p-value <0.05 will be considered significant.

8. Ethical Considerations

Ethical approval was obtained from the institutional ethics committee of Konya City Hospital. Informed consent will be obtained from all patients' legal representatives.

9. Study Timeline

Start of enrollment: July 2025

Estimated primary completion: January 2026

Study end date: February 2026

10. Principal Investigator

Name: [name]

Institution: Konya City Hospital

Email: [contact]

[contact]

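### Is it a flaw that Section 7 relies on a Kolmogorov-Smirnov check and lets the data decide between Pearson and Spearman?

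*Protocol*

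**What the plan says.** Section 7 of the protocol (Statistical Analysis) gives a two-step rule. The first step is "Normality will be assessed via Kolmogorov-Smirnov test". The second is "Correlations will be examined using Pearson or Spearman correlation based on data distribution". The software is SPSS v26, with no procedure named, and the significance threshold is 0.05. The version of the Kolmogorov-Smirnov (K-S) test is not stated: it could use the standard critical value or the Lilliefors correction for an estimated mean and SD.

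Section 6 (Sample Size) rests on one correlation: "Based on a predicted correlation coefficient ($r=0.5$) between RP% and PCT", for which "a power analysis ($\alpha=0.05$, power=0.95) using G*Power resulted in a required sample size of 38"; 42 are to be enrolled. Section 2 (Objectives) does not list the RP%-PCT correlation. The primary objective is diagnostic accuracy. The secondary ones are 28-day mortality, SOFA scores and antibiotic de-escalation.

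**The concern.** Three things catch the eye.

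- At about 40 patients, K-S detects skew less often than Shapiro-Wilk. If it is run uncorrected with mean and SD estimated from the sample, it rarely flags moderate skew at all. Skewed data could then go to Pearson and cost power.
- The coefficient for the correlation that justified the sample size is chosen after the data are seen. Data-driven choice of a test can inflate type I error.
- Pearson and Spearman measure different quantities when a marker is skewed, so a reader cannot say in advance which one will be set against the predicted 0.5.

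At stake would be the power and error rate of the sizing analysis, and the meaning of the reported coefficient.

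**Working it through.** **Inputs.** From Section 6: r = 0.5, alpha 0.05, power 0.95, 38 required, 42 enrolled. From Section 7: K-S of unstated version, then Pearson or Spearman. Assumed, because the protocol gives no distributions: log-normal markers with various log-SDs, Spearman used if either marker fails the check, and two-sided testing.

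**1. The plan's own figure.** The exact bivariate-normal test, one-sided, has power 0.9459 at 37 and 0.9507 at 38, so 38 reproduces. The one-sided Fisher z formula gives ((1.645 + 1.645)/atanh(0.5))² + 3 = (3.290/0.5493)² + 3 = 38.9, that is 39. A two-sided exact test has power 0.909 at 38, which is why the powers below lie near 0.90 and not 0.95. Sidedness is a separate matter.

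**2. Is K-S less sensitive?** Yes. Proportion flagged as non-normal at n = 38:

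| True shape | K-S uncorrected | K-S Lilliefors | Shapiro-Wilk |
|---|---|---|---|
| Normal | 0.0% | 5.0% | 5.5% |
| Log-normal, log-SD 0.5 | 6.3% | 58.5% | 82.9% |
| Log-normal, log-SD 1.0 | 60.7% | 97.2% | 99.9% |

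**3. Does the data-driven choice inflate type I error?** No. With no association, rejection is 4.6% to 5.3% on all routes (20,000 replicates; Monte Carlo standard error √(0.05 × 0.95/20,000) = 0.15 points). The rule looks at the shape of each marker, not at the association between them. Taking the smaller of the two p-values would give 6.5% to 8.7%, but Section 7 does not allow that.

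**4. What does it do to power?** n = 38, latent r = 0.5, two-sided, log-SD pairs in the order RP%, PCT:

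| Shapes | K-S uncorrected | K-S Lilliefors | Shapiro-Wilk | Spearman fixed |
|---|---|---|---|---|
| 0.3, 0.6 | 0.850 | 0.862 | 0.867 | 0.866 |
| 0.3, 0.8 | 0.834 | 0.870 | 0.873 | 0.873 |
| 0.5, 0.6 | 0.829 | 0.863 | 0.869 | 0.870 |
| 0.5, 0.8 | 0.814 | 0.862 | 0.865 | 0.865 |
| 0.5, 1.0 | 0.824 | 0.865 | 0.867 | 0.867 |
| 0.5, 1.3 | 0.846 | 0.867 | 0.867 | 0.867 |
| PCT only, 0.25 | 0.899 | 0.891 | 0.886 | 0.868 |
| PCT only, 0.5 | 0.881 | 0.874 | 0.870 | 0.867 |
| Both normal | 0.906 | 0.900 | 0.900 | 0.866 |

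- Lilliefors against fixed Spearman: the largest loss is 0.870 − 0.863 = 0.7 points. At n = 42 it is at most 0.5.
- Uncorrected against fixed Spearman: the largest loss is 0.865 − 0.814 = 5.1 points. At n = 42 it is at most 4.3. PCT alone can also cause a loss if strongly skewed: with log-SD 1.0 and normal RP%, power is 0.843 uncorrected against 0.867 for both Lilliefors and Spearman.

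**5. Would the alternatives be better?**

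- Spearman fixed, both markers normal: 0.900 − 0.866 = 3.4 points lost against Lilliefors, and 0.906 − 0.866 = 4.0 against uncorrected.
- Shapiro-Wilk in place of Lilliefors: at most 0.869 − 0.863 = 0.6 points gained, and up to 0.891 − 0.886 = 0.5 lost.
- Pearson on logs: about 0.91 if the markers are log-normal, but 0.903 to 0.865 if the raw data are normal with CV 0.15 to 0.30, where raw Pearson has about 0.91.

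**6. Do the two coefficients differ?** Under log-normality, population Pearson is (exp(r·s₁·s₂) − 1)/√((exp(s₁²) − 1)(exp(s₂²) − 1)), where s₁ and s₂ are the two log-SDs. It is 0.466 at (0.3, 0.6), 0.407 at (0.5, 1.0) and 0.343 at (0.5, 1.3). Population Spearman is (6/π)·asin(0.25) = 0.483 throughout. On the Lilliefors route, Pearson is chosen in about 20% of samples at (0.3, 0.6), where the two are close, but in only about 1% at (0.5, 1.0) and 0.1% at (0.5, 1.3), where they differ most.

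**The case for a change.** The best case for the concern is that this is not mere silence. The protocol itself picks the less sensitive test and leaves open the coefficient for the one analysis that produced the sample size. If the uncorrected version is used, up to 5 points of power go, and with moderate skew most samples are analysed with Pearson. One sentence written before the data are seen would remove the doubt.

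The factual parts stand: K-S is less sensitive, the version is unstated, and the coefficient is not fixed. Naming it in advance would be tidy. But the uncorrected version is an assumption and not the protocol's text, and a version number is ordinary analysis-plan content. What Section 7 does commit to, a normality check followed by the matching coefficient, contradicts nothing and yields a valid test. The proposed replacements do not clearly improve on it: each gains or loses according to marker shapes that nobody can read from the protocol.

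**Conclusion.** The concern does not hold. Followed as written, Section 7 keeps type I error close to 5%. With the Lilliefors correction it gives up less than 1 point of power against a Spearman coefficient fixed in advance, and more than 3 points are saved if both markers are normal. The only material loss, about 5 points at worst, depends on an uncorrected K-S test that the protocol never names. The difference between the two coefficients is real under skew, but on the Lilliefors route the rule almost never reports Pearson where that difference is large. The correlation matters for the sample size only and answers none of the listed objectives.

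These figures assume log-normal or normal markers, two-sided testing, and Spearman whenever either marker fails the check. They cover the correlation only, not the group comparisons that Section 7 also mentions.

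### Does the plan need a SOFA-adjusted model before it can report the link between RP% and 28-day mortality?

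*Protocol*

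**What the plan says.** Section 7 (Statistical Analysis) names its methods briefly. Of group comparisons it says: "Comparisons will be made using independent samples t-test or Mann-Whitney U test for continuous variables", with Pearson chi-square for categorical variables. Of associations it says: "Correlations will be examined using Pearson or Spearman correlation based on data distribution". It names no regression or other multivariable method, and it does not rule one out.

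The title announces the "Diagnostic and Prognostic Value of Reticulated Platelet Fraction in Patients With Ventilator-Associated Pneumonia", and Section 1 says: "This study aims to evaluate the diagnostic and prognostic value of RP% in VAP". Section 2 turns the prognostic part into two secondary objectives: "To evaluate the association between RP% and 28-day mortality" and "To explore correlations with SOFA scores and antibiotic de-escalation". Section 5 states that "clinical data (demographics, MV duration, SOFA scores) will be collected from electronic records", without giving a time point for SOFA.

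Section 6 sizes the study on the correlation of RP% with PCT, not on mortality: the calculation "resulted in a required sample size of 38", raised to 42 for dropout.

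**The concern.** RP% may rise with illness severity, and severity predicts death. RP% would then differ between survivors and non-survivors even if it told the clinician nothing beyond the SOFA score. A two-group test cannot separate these situations. The RP%-SOFA correlation can show that the two overlap, but not whether RP% adds anything.

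Prognostic value is often understood as value beyond known predictors. Read that way, the title and Section 1 promise more than Section 7 can deliver, although SOFA is already in the data and one more model would need no new measurements. What would be at stake is a significant crude result presented as evidence that RP% is a useful prognostic marker when it only mirrors SOFA.

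**Working it through.** **1. The plan's own figure.** With r = 0.5, alpha = 0.05 and power = 0.95, the Fisher z formula, one-sided, gives n = ((1.645 + 1.645)/0.5493)² + 3 = 38.9, so 39. The exact bivariate-normal calculation, one-sided, gives 38 (power 0.951); two-sided it gives 46. The stated 38 therefore reproduces one-sided. It concerns RP% and PCT only, and nothing below disputes it.

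**2. Objectives against methods.**

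| Objective (Section 2) | Method available (Section 7) | Answered as worded? |
|---|---|---|
| Association of RP% with 28-day death | t-test or Mann-Whitney of RP% by survival status | Yes, unadjusted |
| Correlation of RP% with SOFA | Pearson or Spearman | Yes |
| RP% beyond SOFA | None listed | Not an objective |

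**3. What the crude test does if RP% adds nothing to SOFA.** The Protocol gives no mortality rate, SOFA effect or RP%-SOFA correlation. Assumed inputs: n = 38 to 42, mortality 30 to 50%, SOFA odds ratio 2 to 4 per SD, RP% and SOFA bivariate normal, no RP% effect given SOFA. Simulated share of studies with crude t-test p < 0.05 (4,000 to 5,000 replicates per cell):

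| RP%-SOFA correlation | Crude test significant |
|---|---|
| 0 | 4 to 6% |
| 0.3 | 8 to 16% |
| 0.5 | 14 to 39% |

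A separate simulation with n = 42 and a SOFA odds ratio of 3 reached 53% at a correlation of 0.7. When the correlation is not zero, RP% really is associated with death in these scenarios. The rejections are correct answers to the stated objective. With no correlation, the test holds its nominal level.

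Among the crude-significant studies at correlations 0.3 to 0.5, 66 to 94% lose significance once SOFA enters a Firth-penalised model; a repeat with an ordinary likelihood-ratio test gave 53 to 92%. That is expected, because the simulation gave RP% no added effect.

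**4. What the planned RP%-SOFA correlation contributes.** Its power is Φ(atanh(r)·√(n − 3) − 1.96).
- r = 0.3: Φ(0.3095 × 5.916 − 1.96) = 0.449 at n = 38, and 0.489 at n = 42.
- r = 0.5: 0.901 and 0.929.

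The relevant studies are those where the crude test is significant. Among these, the correlation is non-significant in 17.9 to 33.8% at r = 0.3 and in 1.1 to 5.4% at r = 0.5. It therefore signals the overlap in 66 to 82% and in 95 to 99% of them. Multiplying the largest values gives an upper bound on a significant crude result with no such signal:
- r = 0.3: 0.164 × 0.338 = 0.055, about 6% of studies.
- r = 0.5: 0.388 × 0.054 = 0.021, about 2%.

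**5. What an adjusted model could settle.** Deaths: 38 × 0.3 = 11.4 to 42 × 0.5 = 21, enough for two terms at most. At 20% mortality there would be 7.6 to 8.4 deaths, about 4 per term. If RP% truly carried an independent odds ratio of 2 per SD, the adjusted test would detect it in 24 to 42% of studies and miss it in 58 to 76%. The upper confidence limit for the odds ratio would be about 4 to 9 times the lower.

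**The case for a change.** The best case for the concern is that the title and aim use a stronger term than the objective does, and that a significant crude test under that title invites the stronger claim. Section 7 names its tests without pointing to a further analysis document. A model fixed before outcomes are seen is worth more than one added later, and it needs no new data. The correlation is also an imperfect guard: an observed r of 0 would have a 95% interval of about ±0.32 at n = 38 (tanh(1.96/√35)) or ±0.30 at n = 42, so it could not exclude 0.3.

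The factual part stands: every listed method is unadjusted, and none can show that RP% adds to SOFA. The step from there to a defect does not. The objectives, not the title, define what is to be estimated, and Section 2 defines an association. Nothing in the Protocol announces a claim of value beyond severity, so the harm depends on a later report going further than the plan. A covariate-adjusted exploratory model for a secondary objective is also what a protocol commonly leaves to the statistical analysis plan. That plan is not at hand, and the Protocol's silence does not show that no such model is planned.

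**Conclusion.** The concern does not hold. The methods in Section 7 are valid for the mortality and SOFA objectives as Section 2 words them, and carrying them out as written gives a sound, unadjusted answer. The Protocol states nothing wrongly here and does not contradict itself. A SOFA-adjusted model would add a new question rather than correct an error, and with about 11 to 21 deaths it would seldom settle that question.

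This conclusion rests on the wording of Section 2, not on the simulations. All simulated figures depend on assumed mortality, SOFA effect and RP%-SOFA correlation; they show only that the crude test behaves properly and that the planned correlation gives a partial warning of overlap. The limit to keep in mind is one of interpretation: the listed methods support a statement about association with death, not one about prognostic information beyond SOFA.

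### The only primary objective is diagnostic accuracy of RP%, but the methods in Section 7 give no accuracy estimate with an interval

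*Protocol*

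**What the plan says.** Section 2 (Objectives) lists one primary objective: "To assess the diagnostic accuracy of RP% in patients with VAP". Association with 28-day mortality, and correlations with SOFA and antibiotic de-escalation, are secondary.

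Section 7 (Statistical Analysis) names these methods:

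- Distribution check: "Normality will be assessed via Kolmogorov-Smirnov test".
- Group comparisons: "Comparisons will be made using independent samples t-test or Mann-Whitney U test for continuous variables, and Pearson chi-square for categorical data". The groups to be compared are not named.
- Association: "Correlations will be examined using Pearson or Spearman correlation based on data distribution".
- Criterion: "A p-value <0.05 will be considered significant".

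The protocol nowhere mentions a cut-off for RP%, sensitivity, specificity, predictive values, a likelihood ratio, a ROC curve or AUC, or a confidence interval. Section 6 (Sample Size) also rests on a correlation: "Based on a predicted correlation coefficient ($r=0.5$) between RP% and PCT". Section 4 (Population) makes a VAP diagnosis an inclusion criterion, and no VAP-negative group is described.

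**The concern.** A diagnostic accuracy objective is answered by a number, such as the share of diseased patients the marker detects at a given cut-off, with its uncertainty. A t-test, a Mann-Whitney p-value, a chi-square test or a correlation answers a different question: whether averages or proportions differ, or whether two measurements move together. A marker can pass any of these tests and still classify patients poorly.

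If Section 7 is followed as it stands, the report will hold p-values and correlation coefficients and no estimate for the primary objective. A cut-off chosen after the data are seen would then be the obvious way to produce one, and it would tend to flatter the marker.

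**Working it through.** **1. The plan's own figure.** The only statistical target in the protocol is the 38 patients of Section 6 (r=0.5, alpha 0.05, power 0.95). Exact bivariate-normal power for a test of zero correlation reaches 0.951 at n=38 with one-sided alpha, so 38 is reproduced on that basis (two-sided would need 46; this is a separate matter). Enrolment of 42 allows for (42−38)/42 = 9.5% dropout. The figure is the size needed for a correlation p-value. It implies no precision for any accuracy measure.

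**2. Objective against method.**

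| Section 2 objective | What Section 7 offers | Accuracy estimate with interval? |
|---|---|---|
| Primary: diagnostic accuracy of RP% | No method assigned; tests and correlations only | No |
| Secondary: association with 28-day mortality | t-test or Mann-Whitney | Tests association; no measure of discrimination with an interval |
| Secondary: correlations | Pearson or Spearman | Not needed |

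**3. What the enrolled cohort can support.** Every patient has VAP. Sensitivity needs only patients with the disease, so it can be estimated. Specificity and an AUC for VAP need patients without VAP. Predictive values need both groups. None of these three can be estimated here, whatever Section 7 says.

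**4. Precision of sensitivity.** Assume 42 analysed patients, 34 of them above the cut-off (illustrative; the protocol predicts no sensitivity). Then p = 34/42 = 0.8095, z = 1.96 and z²/n = 3.8416/42 = 0.0915.

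- Wilson centre = (p + z²/2n)/(1 + z²/n) = (0.8095 + 0.0457)/1.0915 = 0.7836.
- Half-width = 1.96 × √(p(1−p)/n + z²/4n²)/(1 + z²/n) = 1.96 × √(0.003671 + 0.000544)/1.0915 = 0.1166.
- 95% CI = 0.667 to 0.900.

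The Clopper-Pearson interval for the same count is 66% to 91%. If only 38 patients are analysed, 30/38 (79%) has a Clopper-Pearson interval of 63% to 90%.

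**5. What p=0.05 means for discrimination (secondary objective only).** Assume 42 analysed patients and 8 to 21 deaths; the protocol gives no mortality rate. Since U/(n₁n₂) is the empirical AUC, a Mann-Whitney result just at two-sided p=0.05 (normal approximation) corresponds to

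AUC = 0.5 + 1.96 × √(n₁n₂ × 43/12)/(n₁n₂).

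| Deaths/survivors | n₁n₂ | AUC at p=0.05 |
|---|---|---|
| 8/34 | 272 | 0.725 |
| 10/32 | 320 | 0.707 |
| 13/29 | 377 | 0.691 |
| 17/25 | 425 | 0.680 |
| 21/21 | 441 | 0.677 |

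Example for 21/21: √(441 × 43/12) = 39.75; 1.96 × 39.75/441 = 0.177; AUC = 0.677. Hanley-McNeil 95% lower limits across these splits are 0.509 to 0.514. Under an equal-variance binormal model, the point where sensitivity equals specificity is about 63% to 66%.

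**The case against.** **The SAP is not shown.** Accuracy measures, cut-off rules and interval methods are often left to it, and Section 7 is a short paragraph that does not claim to be exhaustive. This stands as a limit: one cannot say that no accuracy estimate will ever be produced. It does not remove the point. Section 7 does not defer to another document. It names the software and the individual tests, and those tests do not match the primary objective.

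**Mann-Whitney is the AUC in another form.** This is correct, and step 5 of the working uses it. But the plan commits to the test at p<0.05, not to reporting the AUC with an interval. In a cohort of VAP patients only, the test can compare groups within VAP, such as deaths and survivors, but not VAP with no VAP.

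**Significance is not equated with value.** A reader might infer that p<0.05 is meant to stand in for clinical or diagnostic value. The protocol does not say so; it says only what will be called significant. That inference is not part of this point.

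**The population is the tighter constraint.** A reader might also treat the analysis problem as separate from who is enrolled, and expect a rewritten Section 7 to deliver full diagnostic accuracy. Section 4 rules that out. Sensitivity alone is also a weak summary, because a low enough cut-off gives 100% sensitivity with no discrimination. This objection stands, and it is why the cut-off must be fixed beforehand and the conclusion limited.

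**Mortality needs only an association.** Section 2 asks for no more than that, and a Mann-Whitney test can address it. The AUC figures therefore do not measure the failure on the primary objective. They show only that significance says little about discrimination.

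**Conclusion.** The point holds as a mismatch between the primary objective and the stated methods: Section 7 as written gives no accuracy figure with an interval. That rests on the protocol text alone, with no numerical assumption.

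The sizes are illustrations. Sensitivity of 81% would carry an interval of 67% to 90%, assuming 34 of 42. For mortality, significance could be reached at an AUC of about 0.68 to 0.72, assuming 42 analysed patients and 8 to 21 deaths; this concerns a secondary objective. Because all patients have VAP, the attainable primary result is sensitivity, not full diagnostic accuracy.

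**What to change.** 1. In Section 7, define the primary result as the sensitivity of RP% at one cut-off fixed before the data are seen (for example the laboratory's upper reference limit), with a Wilson 95% CI. State plainly that specificity, predictive values and an AUC for VAP cannot be estimated in a cohort of VAP patients only, and that the primary conclusion is limited to sensitivity.
2. For 28-day mortality, report the AUC of RP% with a 95% CI beside the AUCs of CRP, PCT and SOFA, which Section 5 already collects. Keep the t-test, Mann-Whitney, chi-square and correlation p-values as supportive.

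Cost: a few lines in Section 7, with no new patients or measurements. The downside is that the intervals will be wide and look less favourable than a single p-value. An AUC for VAP becomes possible only if a non-VAP comparator is added; that is a separate design change with its own recruitment cost, not covered by this estimate.
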